### **Randomization**

This will be an open-label randomized trial with parallel groups. An online service (<http://www.clinapsis.com>) will be used to generate a randomised sequence for the block of 1000 participants.

The allocation will be sequestered internally by a Clinical Trials Unit. After enrolment, recruiting physicians will obtain the allocation group from the Unit. Due to the nature of the interventionism it is not possible to blind participants or physicians from the Obstetric Department; however, obstetric management will follow similar protocols in each of the participating centers.

### **Data collection and analysis**

Study duration:

18 weeks maximum follow-up per patient, taking into account the period of intervention (5weeks) and puerperium (6 weeks) and follow-up visit at 6 months, assuming patients would delivery at less than 42 weeks of gestation. Recruitment will extent for 24 months (Figure 2).

Database: Data of participants included in the study will be codified and entered into an electronic case report form (<http://www.clinapsis.com>). All women included in the trial, independently on their randomization group, will provide a self-reported lifestyle questionnaires to measure anxiety and perceived stress (State-trait Anxiety Inventory-STAI(Spielberger 2010), Perceived Stress Scale-PSS(Cohen, Kamarck, and Mermelstein 1983), WHO Five Well Being Index(Bech et al. 2003)(Bonnín et al. 2018). Trained and certified research staff members will abstract information from medical records, including demographic information, medical history, and outcome data. Participants will be followed up with an interview performed by research personnel immediately and at 4-8 weeks post partum. During this inter- view, women will be asked to rate their experiences on the Labor Agency Scale (Hodnett 1987). A specific database will be designed for the study in order to protect patient confidentiality and register adequately all data for analysis; this database will be designed by the Bioinformatics Unit of the Epidemiology and Preventive Medicine Department of Sant Pau Hospital.

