### Objectives

To evaluate the impact of a policy of induction of labour from 37 weeks of gestation in nulliparous women at risk for preeclampsia as defined by a sFlt1/PIGF ratio >90th centile at 35-36 weeks of gestation on the prevalence of term PE.

As secondary objectives, the study will evaluate the impact of the sFlt1/PIGF screening on:

1. Cesarean section rates
2. Perinatal morbidity
3. Maternal pregnancy-related morbidity.
4. Maternal post-pregnancy endothelial function.
5. Cost-efficiency analysis (hospital maternal and neonatal stay and incurred costs).
6. Maternal experience.

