**Outcome variables**

Main outcome variables: development of term preeclampsia.

Secondary outcome variables:

- Caesarean section rate
- Incidence of perinatal complications defined as the presence of placental abruption, severe fetal growth restriction (defined as birth weight <3rd centile), perinatal mortality, an Apgar score at 5-minute below 7.0, an umbilical artery pH below 7.10, need for respiratory support within 72 hours after birth neonatal intraventricular haemorrhage grade III/IV, necrotizing enterocolitis, periventricular leukomalacia, sepsis, bronchopulmonary dysplasia or hypoxic ischemic encephalopathy.
- Incidence of maternal complications, defined by a composite including any of the following: (i) HELLP syndrome (lactate dehydrogenase [LDH] >700 IU/L, AST to twice normal values and platelet count <100x10^9/L); (ii) Central nervous system dysfunction (eclampsia, Glasgow Coma Score <13 (12), stroke, reversible ischemic neurological deficit or cortical blindness); (iii) hepatic dysfunction (INR >1.2 in the absence of disseminated intravascular coagulation, MELD score >10 (16), or hepatic hematoma or rupture); (iv) renal dysfunction (dialysis, serum creatinine concentration greater than 150 µmol/L, or urine output <0.5 mL/kg/h during 12 hours, according to renal insufficiency by RIFLE criteria; or need for treatment with furosemide to maintain urine output >0.5 mL/kg/h for 3 hours); (v) respiratory dysfunction (pulmonary edema, requirement of invasive or non-invasive mechanical ventilation, oxygen requirement greater than 50% concentration for longer than 1 hour, or severe breathing difficulty [no criteria of pulmonary edema but presence of dyspnea, crackles in pulmonary auscultation, and SaO2<90%]); (vi) cardiovascular dysfunction (need for inotropic support, left ventricle failure, or myocardial infarction); (vii) placental abruption; or, (viii) a requirement for transfusion of blood products.
- Maternal blood pressure and endothelial function 6-months postpartum.
- Maternal and neonatal hospital stay duration (days).
- Maternal satisfaction and experience assessed by questionnaires (PSS, STAI, WHO and Labor Agency scale).

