### **Statistical analysis**

Once all evaluations have been performed and laboratory determinations have been completed, the evaluation and analysis of the results will be carried out, with assistance of the Bioinformatics Department of the Institut de Recerca, and the Research Support Unit. Statistical analyses will be performed with the statistical package IBM® SPSS® Statistics Version 25 (IBM Corporation) or Open-source software (The R Foundation for Statistical Computing) will be used for all computations and graph construction (R V2.15.1). Statistical analysis will be based on the originally assigned groups (intention-to-treat). Normality of the distribution of variables will be evaluated with the Kolmogorov-Smirnov test. A binomial distribution model will be used to determine the 95% CI of proportions. Student's t-test (or non-parametric Mann-Whitney U test) and Pearson's  $\chi^2$  test or linear-by-linear  $\chi^2$  test (for trends across ordered categories) will be performed for univariate between-group comparisons of quantitative or qualitative variables, respectively. A mixed-effects logistic regression analysis of the incidence of live-birth with fixed effects for allocation group will be

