### 1. USE OF PERSONAL DATA

Patients' information involved in the project will be managed under the rules for processing of personal data, as required by the European Directive 95/46/EC. According to this directive, the coordinator of the project is defined here as controller of data. Particularly, the following principles will be observed through appropriate measures:

- a) Legitimate acquisition and processing:
  - The information recorded will be relevant and not excessive, in accordance with the purposes of the objectives of the study, explicitly expressed in the information to patients.
  - The data will be processed only for the purposes defined in the study.
  - Unambiguous written consent will be obtained by the data subject in all cases.
- b) Information given to the data subject: the Informed Consent texts include clear information and purposes of the processing.
- c) The consent form will explain that if a participant wishes to withdraw from the study the data and samples acquired prior to that point will be retained. Reason for withdrawal will be recorded, if given, as will loss to follow up.

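### Does the stated 18-week maximum follow-up put the visit at 6 months postpartum at risk?

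*Protocol*

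**What the plan says.** The study-duration paragraph of the Protocol (Data collection and analysis) sets "18 weeks maximum follow-up per patient, taking into account the period of intervention (5weeks) and puerperium (6 weeks) and follow-up visit at 6 months", and adds the condition "assuming patients would delivery at less than 42 weeks of gestation". The same section gives 24 months of recruitment and an interview at 4 to 8 weeks after delivery.

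The Outcome variables section lists, as a secondary outcome, "Maternal blood pressure and endothelial function 6-months postpartum". The matching secondary objective, under Objectives, is "Maternal post-pregnancy endothelial function". The Statistical analysis section starts the analysis "Once all evaluations have been performed and laboratory determinations have been completed". The synopsis gives a total duration of 3 years.

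**The concern.** One sentence sets a ceiling of 18 weeks and says that the ceiling allows for a visit at 6 months. Six months is about 26 weeks, so the visit lies outside the ceiling for every participant.

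That visit is the only stated time point for the blood pressure and endothelial function outcome. If a centre took 18 weeks as the end of participation, it might not recall women for the visit. Centres might also differ on whether a woman seen at 4 to 8 weeks but not at 6 months had finished the study or been lost. With many centres in four countries, such differences could leave uneven missing data on one secondary outcome.

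**Working it through.** **Inputs**
- Enrolment: 35+0 to 36+6 weeks (Inclusion and Exclusion Criteria).
- Delivery: from 37+0, when induction is first offered (synopsis, Intervention), to 41+6, the last day before 42 weeks (study duration).
- Visit: 6 months after delivery (Outcome variables). Assumption: 6 months = 365.25 / 2 = 182.6 days = 26.1 weeks.

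**Can 18 weeks be reproduced?**

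| Reading | Sum (weeks) |
|---|---|
| Intervention + puerperium | 5 + 6 = 11 |
| 35+0 to 42+0, + puerperium | 7 + 6 = 13 |
| Intervention + latest interview | 5 + 8 = 13 |
| 35+0 to 42+0, + latest interview | 7 + 8 = 15 |
| 6 months counted from enrolment | 26 |
| Intervention + 6 months | 5 + 26 = 31 |
| 35+0 to 42+0, + 6 months | 7 + 26 = 33 |
| Intervention + puerperium + 6 months | 5 + 6 + 26 = 37 |

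None gives 18. Every reading without the visit is below 18, and every reading with it is at least 26.

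**When the visit falls**

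Time from enrolment = (gestational age at delivery − gestational age at enrolment) + 26.1 weeks.
- Earliest: enrolled 36+6, delivered 37+0. 1 day = 0.1 week; 0.1 + 26.1 = 26.2 weeks; 26.2 − 18 = 8.2 weeks over.
- Latest: enrolled 35+0, delivered 41+6. 48 days = 6.86 weeks; 6.86 + 26.09 = 32.9 weeks (32.95 before rounding); about 14.9 weeks over.

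A spontaneous delivery before 37+0 could bring the earliest case down to about 26.1 weeks, but never below 26.

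**Does it fit the overall timeline?**

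33 weeks × 7 / 30.44 = 7.6 months. 24 + 7.6 = 31.6 months, inside 36.

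**What depends on the figure?**
- Sample size: the calculation uses event proportions, alpha, power and a 10% loss allowance. Follow-up time is not an input.
- Primary outcome: term preeclampsia does not depend on the 6-month visit. Nor do caesarean section or the delivery and neonatal outcomes.
- Analysis: its start is tied to completed evaluations, not to elapsed weeks.
- Completion and loss: the data-protection section says "Reason for withdrawal will be recorded, if given, as will loss to follow up". This is part of what the consent form explains about withdrawal. It defines neither completion nor loss and does not mention 18 weeks.

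**The case for a change.** The strongest case for acting is that follow-up length and end of participation belong in a protocol, so the matter cannot be left to an analysis plan. Here the stated figure conflicts with the protocol's own visit schedule. The correction would be wording only, and it would remove any doubt about when a woman has finished the study.

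Part of this stands. The sentence does not add up, and an editor would correct it. A less natural reading takes 18 weeks as a core period around birth with the 6-month visit as an addition. All other stated contacts fit inside that, at 15 weeks at most. But the text calls 18 weeks a maximum and lists the visit among the things allowed for, so the wording does not support this reading well.

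The harm does not stand. For a centre to drop the visit because of this sentence, it would have to follow the number and ignore the visit named beside it, the outcome list and the objective. The argument that centres would classify losses differently joins the 18 weeks to the data-protection item, and the Protocol makes no such link. The timeline figure cited in the paragraph is not shown here and may set out the visits. It would not cure the sentence, but it is a further reason not to presume how centres understood the schedule.

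**Conclusion.** The arithmetic point is correct. A maximum of 18 weeks cannot contain a visit that falls about 26 to 33 weeks after enrolment, and no sum of the stated parts gives 18. This rests on 6 months being about 26 weeks, counted from delivery as the outcome list says, and on delivery between 37+0 and 41+6.

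No change to the plan follows. It is a clerical slip in a descriptive sentence. The visit is required elsewhere in clear terms, with its own time origin, and fits the 3-year duration at about 31.6 months. No estimate, error rate, power figure or analysis set would differ if the number were put right. A colleague running the trial or analysing the data would schedule and use the visit at 6 months postpartum either way.

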**PE37: A multicenter randomized trial of screening with sFlt1/PIGF and selective labor induction to prevent preeclampsia at term.**

Primary Site:
 
BCNatal (Hospital Clínic and Hospital Sant Joan de Déu) and Hospital Sant Pau, Barcelona, Spain

Principal Investigators:
 
[name], [name] and [name]

Disease Studied and Intervention
 
Preeclampsia in late pregnancy

Cohort:
 
Non-selected nulliparous pregnant women routinely attended at 35-36 weeks' gestation and randomized to revealed versus concealed maternal angiogenic factors levels.

Inclusion and Exclusion Criteria:
 
Inclusion criteria:
 
 
1. Nulliparous women
 
2. Singleton pregnancies
 
3. >18 years old
 
4. 35.0-36.6 weeks of gestation
 
5. Maternal written consent form
 
6. Planned vaginal delivery
 
 
Exclusion criteria:
 
-Any maternal or fetal complications that require labor induction before 38 weeks according to local institutional protocols (including established preeclampsia).

Study Type
 
Prospective, open-label randomized multicentre study with parallel groups conducted at BCNatal (Hospital Clínic and Hospital Sant Joan de Deu) (Barcelona), Hospital Sant Pau (Barcelona), Hospital la Paz (Madrid), Hospital del Mar (Barcelona), Hospital la Fe (Valencia), Hospital Son Llatzer (Mallorca), Hospital Can Ruti (Badalona), Hospital Clínico de Zaragoza, Hospital Arrixaca de Murcia and Complejo Hospitalario Universitario Insular Materno Infantil (Las Palmas de Gran Canaria) (Spain), Institute for the Care of Mother and Child, Prague, Prague, Czechia, Centre of Postgraduate Medical Education, Obstetrics and Gynecology and Perinatal Medicine, Warsaw, Poland;

Gynecology and Obstetrics - CHU Liège; Belgium.

Intervention
 
 
Revealed arm: Blood sampling at 35+0-36+6w to determine sFlt-1/PlGF ratio. The result will be known by managing clinicians and, if >90th centile, labour induction from 37+0 weeks will be offered.
 
Concealed arm: The result of sFlt1/PlGF ratio will be unknown. Routine follow-up
 

Duration
 
3 years

Date Of First Enrolment
 
February 2021

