
Estimated Sample Size
 
8302 nulliparous women are needed to demonstrate a 50% reduction of development of PE (from 1.5%) with a 90% power and a 5% alpha-risk. Assuming a 10% loss, we estimated a sample size of 9132 women.

Study Aims
 
To evaluate the impact of a policy of induction of labour from 37 weeks of gestation in nulliparous women at risk for preeclampsia as defined by a sFlt1/PlGF ratio >90th centile at 35-36 weeks of gestation on the prevalence of term PE.
 
As secondary objectives, the study will evaluate the impact of the sFlt1/PlGF screening on:
 
 
Cesarean section rates
 
Perinatal morbidity
 
Maternal pregnancy-related morbidity.
 
Maternal post-pregnancy endothelial function.
 
Cost-efficiency analysis (hospital maternal and neonatal stay and incurred costs).
 
Maternal experience.
 

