## **Background**

### **Preeclampsia at term as an unsolved problem with a high health impact**

Preeclampsia (PE), defined as the presence of hypertension with other signs of endothelial systemic damage, affecting 5-10% pregnancies and remains one of the most prevalent serious complications of pregnancy. Despite improved obstetrical care, PE remains a leading cause of maternal morbidity and mortality worldwide. While early-onset PE is the most feared form of the disease, a remarkable 70% of total cases occur at term (1), accounting for a large proportion of adverse maternal outcomes (2). Identification of term PE relies on clinical follow up and detection of hypertension in a pregnant woman, followed by elective delivery. This policies have been shown to reduce the rates of severe maternal complications and is now standard practice (3), but still result in a significant proportion of

cases detected too late (4). One important reason is that most instances of term PE occur in women without risk factors. Aside from the rates of severe complications, the diagnosis of PE entails a traumatic experience for women affecting their pregnancy and birth experience and their pathway to motherhood (5) (6). Moreover, PE has a significant impact in healthcare costs (7) and suffering PE predisposes women for long-term cardiovascular adverse outcomes later in life.

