#### **Angiogenic factors: PlGF and sFlt1 and their role as specific biomarkers of PE**

For more than 100 years, PE was diagnosed by hypertension and proteinuria in a pregnant woman. Angiogenic factors have recently emerged as the most specific biomarkers of PE ever described, so much that are being incorporated as an essential component in the prediction, diagnosis and even prognosis of PE by all relevant international societies.

Under normal conditions, angiogenic factors released by the placenta maintain a balance in maternal blood whereby the effects of the proangiogenic Placental Growth Factor (PlGF) prevail over those of the antiangiogenic soluble fms-like tyrosine kinase 1 (sFlt1). In preeclampsia, placental inflammation and increased oxidative stress result in the release of larger amounts of sFlt1 over PlGF. Thus, the ratio sFlt1/PlGF reflects placental and endothelial functioning, the end-organs of preeclampsia, and it is a consubstantial feature of the disease.

This ratio has now been accepted as a criterion for the diagnosis of PE in suspected cases (12). According to recent studies in large populations, the capacity of an abnormal ratio in ruling-in the disease is intermediate-large (as reflected by a +LHR of 8.2), while its capacity in ruling it out is large (–LHR 0.2). This is in line with the high performance shown by the sFlt1/PlGF ratio to predict term PE at 35-36w. Thus, the sFlt1/PlGF ratio might represent a

feasible universal approach for the detection of risk by identifying term PE in its pre-clinical stages.

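### The protocol does not say that the staff who record preeclampsia are masked, so classification of borderline cases can differ by arm, in either direction

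*Protocol*

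**What the plan says.** - **Masking.** The Randomization section says "This will be an open-label randomized trial with parallel groups" and that, because of the nature of the intervention, "it is not possible to blind participants or physicians from the Obstetric Department". It says nothing about anyone else.
- **Who records outcomes.** The Data collection and analysis section gives this to a different group: "Trained and certified research staff members will abstract information from medical records, including demographic information, medical history, and outcome data". Their masking status is not stated. No endpoint committee or masked adjudication is described anywhere in the protocol.
- **Primary outcome.** The Outcome variables section has only "Main outcome variables: development of term preeclampsia", with no blood-pressure, proteinuria or laboratory thresholds. The maternal composite in the same section has detailed thresholds. The nearest thing to a definition is a general description in the Background: "defined as the presence of hypertension with other signs of endothelial systemic damage".
- **The ratio.** The Background section on angiogenic factors says "This ratio has now been accepted as a criterion for the diagnosis of PE in suspected cases". In the synopsis, under Intervention, the revealed arm is the one in which "The result will be known by managing clinicians"; in the concealed arm it is unknown.

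**The concern.** The stated obstacle to masking applies to the women and to the obstetricians who manage them. It does not apply to staff who read records and fill in a form, yet the protocol does not use that opportunity.

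This trial is more exposed than most open-label trials. The randomised element is a piece of information that the protocol itself treats as part of the diagnosis. For a woman with borderline hypertension, a low ratio in view may discourage a PE label and a high one may encourage it. In the concealed arm neither influence exists. Without written criteria there is room for that judgement to operate.

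The primary comparison is planned on fewer than 100 events, so a shift of a few cases matters. Randomisation and intention-to-treat analysis do not correct for classification that depends on the arm.

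**Working it through.** **1. Reproduce the plan's own figure.** The synopsis states "8302 nulliparous women are needed to demonstrate a 50% reduction of development of PE (from 1.5%) with a 90% power and a 5% alpha-risk". The code under Sample size calculation uses 0.0075 and 0.015 with a 1:1 ratio. The unpooled two-proportion formula with two-sided 5% gives

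n per arm = (1.960 + 1.282)² × [0.0075 × 0.9925 + 0.015 × 0.985] / 0.0075² = 10.507 × 0.02221875 / 0.00005625 = 4150.4.

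This rounds up to 4151 per arm and 8302 in total, which matches exactly. A one-sided test gives 6766, so the two-sided reading is the right one.

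**2. Expected events.** 4151 × 0.015 = 62.3 in the concealed arm and 4151 × 0.0075 = 31.1 in the revealed arm: about 62 v 31.

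**3. Under-recording in the revealed arm when there is no true effect.** The fraction f is an assumption; no such figure is in the documents. Take true PE as p₂ = 0.015 in both arms and the recorded revealed rate as p₁ = 0.015 × (1 − f). The chance of a significant result favouring the revealed arm is

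Φ{[(p₂ − p₁) − 1.96 × SE₀] / SE₁},

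where SE₀ is the pooled and SE₁ the unpooled standard error at 4151 per arm. For f = 10%, p₁ = 0.0135, the difference is 0.0015 and both standard errors are 0.00260. The argument is (0.0015 − 0.00510) / 0.00260 = −1.383, and Φ = 8.3%.

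| Net under-recording f | Cases shifted, of about 62 | Chance of a false significant benefit |
|---|---|---|
| 0 | 0 | 2.5% |
| 5% | 3.1 | 4.7% |
| 10% | 6.2 | 8.3% |
| 20% | 12.5 | 21.9% |

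**4. Over-recording in the revealed arm when the planned effect is real.** The true rates are 0.75% v 1.5%, and the recorded revealed rate is 0.0075 × (1 + f). The same formula gives power of 90.0% at f = 0, 81.8% at f = 10% (recorded 0.825%) and 70.9% at f = 20% (recorded 0.90%).

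**5. How large a shift is significant without help from chance.** With 62 concealed-arm cases, the revealed arm must fall to 42 for an uncorrected chi-square p of 0.048. That is 20 of 62 cases, or 32%.

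**6. How demanding the shifts in step 3 are.** Table 1 of the protocol gives detection rates of 62% (within 4 weeks) and 82% (within 2 weeks) at a 10% screen-positive rate. Used as a rough guide, they leave 62.3 × 0.38 = 23.7 or 62.3 × 0.18 = 11.2 of the revealed-arm cases screen-negative. If only screen-negative cases lose their label, a net 10% shift needs 6.2/23.7 = 26% or 6.2/11.2 = 56% of them to go unrecorded. A net 20% shift needs 12.5/23.7 = 53%, or more than all of the 11.2.

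**The case against.** Four objections deserve weight.

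- **The abstractors may in fact be masked.** A reader might infer that they are unmasked. The protocol does not say so: it is silent, and it names only managing clinicians as knowing the ratio. What stands is an omission. It is still one for the protocol to close, because who assesses the primary outcome, and with what knowledge, is a design feature rather than a detail for the analysis plan.
- **The direction is not known.** A reader might infer that the bias favours the intervention. The protocol's own figures point at least partly the other way. At 62% to 82% detection most revealed-arm PE cases would be screen-positive, and a known high ratio that counts towards the diagnosis could add PE labels. This objection stands in full, which is why step 4 is shown beside step 3.
- **The size is assumed, and the upper values are hard to reach.** This also stands. Step 6 shows that a 20% net shift would need very heavy under-recording among screen-negative women, and at 82% detection it could not come from them alone. Even at 10%, a false significant benefit fails to appear about 92% of the time.
- **Masking abstractors does not mask the clinicians.** Obstetricians who know the ratio decide what to measure and what diagnosis to write. Masked staff who copy that diagnosis would gain little. This stands against masking alone. It does not stand against classifying from recorded values under written criteria.

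**Conclusion.** The point holds as a gap in the design. As written, the protocol allows the primary outcome to be classified with knowledge of the arm and the ratio, because it neither requires masking of the abstractors nor defines PE operationally.

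The size is illustrative. It rests on true PE of 1.5% in both arms, 4151 per arm, a two-sided 5% test and an assumed net under-recording of 5% to 20%, and gives a false-benefit risk of 4.7% to 21.9% against the nominal 2.5%. In the other direction, 10% to 20% over-recording in the revealed arm would cut power for the planned effect from 90% to between 82% and 71%.

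A reader might also infer that a modest recording difference would by itself produce a positive trial. The arithmetic does not support that: without help from chance it takes about 20 of 62 cases. A smaller shift changes the probability of a wrong conclusion; it does not determine the result.

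**What to change.** Amend three sections of the protocol.

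- **Outcome variables:** add written criteria for term PE that do not use the sFlt1/PlGF ratio.
- **Data collection and analysis:** state that for every woman with hypertension after randomisation, the blood pressure, proteinuria and laboratory values are entered in the electronic case report form.
- **Randomization, and Data collection and analysis:** state that PE for the primary analysis is classified from those coded values by the existing research staff, with arm, ratio and reason for induction hidden on the form. The treating team's diagnosis is used as a sensitivity analysis.

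The cost is a little more data entry for hypertensive women and hidden fields in the form. Working from coded values avoids redacting notes and needs no additional reader. Treatment and sample size do not change. One limit remains: differences between arms in how often women are measured or tested are not removed, because the clinicians who order the tests cannot be masked.
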